### 2.1.3 Retention and Engagement Strategies

To ensure sustained participation throughout the follow-up period, the research team will implement continuous engagement measures using multiple digital communication channels, including the Zalo application, SMS, telephone calls, and support from community peer leaders. Participants will be contacted regularly to receive project updates, appointment reminders, and encouragement to take part in each data-collection round. Ongoing assistance will also be provided to help maintain participants' motivation and consistency in completing questionnaires. For the STOS group, follow-up communication will additionally ensure that participants receive their self-testing kits. These combined strategies are expected to achieve follow-up retention rates exceeding 80% at each assessment point.

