## 2.3 Consent

### 2.3.1 Consent Procedures

All participants will provide informed consent by clicking "accept button" at the time they begin the online survey. For participants under 18 years of age, a waiver of parental consent will be obtained from the ethics committee to protect them from the potential risk of unintentional

disclosure of their sexual orientation or HIV status. Before joining the study, participants will receive a study information sheet explaining the research objectives and procedures. This document will appear immediately before the consent question in the online survey, allowing participants to review the study details before providing consent. After completing the survey, participants who are interested in joining the STOS intervention will be introduced to additional information, as follows: Participants will be informed that the study involves an online HIV self-testing intervention and that they may be randomly assigned to one of two testing approaches.

The first approach involves receiving an HIV home self-testing kit, with real-time guidance and support from trained staff via video calls and instructional videos. The second approach involves receiving information about free HIV testing services available at public hospitals, where participants can go for testing independently. If selected for participation, study staff will contact participants using the contact information provided to explain further details and confirm their willingness to take part. For those who are randomly assigned to the STOS group, multiple formats will be used to ensure a full understanding of study procedures. These include printed materials, instructional videos (e.g., how to perform HIV self-testing), and verbal explanations provided by trained counsellor. Participants will be encouraged to ask questions about any aspect of the study, including the survey process, HIV self-testing procedures, and their right to withdraw from the study at any time without penalty or loss of benefits. Informed consent will be obtained only after participants demonstrate clear understanding and express their willingness to participate voluntarily. At each follow-up round, field staff will reassess participants' understanding and verbally reconfirm consent before administering questionnaires or conducting STOS sessions, to ensure that participants remain fully informed and voluntarily engaged throughout the longitudinal study

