#### 2.4.2 Primary and Secondary Outcome Analyses

To evaluate the effects of the STOS intervention, two groups will be compared: the STOS group, who receive an HIV self-testing kit and complete the online questionnaires, and the control group, who complete the questionnaires only. The primary outcomes are the rate of HIV testing uptake and the rate of new HIV infections during the study period. The secondary outcomes include changes in sexual behaviors, mental health, and other psychosocial indicators over time. To assess the effects of the intervention across time points, Generalized Estimating Equations (GEE) models will be applied, using a log link function for rate outcomes and an identity link function for continuous outcomes. The models will include variables for study arm (STOS vs. control), time (follow-up round), and their interaction term (arm  $\times$  time) to estimate longitudinal intervention effects. Robust standard errors will be used to account for within-subject correlation due to repeated measures. The results will be presented as Rate Ratios (RRs or Incidence Rate Ratios, IRRs) with 95% confidence intervals (CIs) and p-values to indicate the magnitude and statistical significance of the observed effects.

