## 2.5 Assessment and management of risk

This study will be conducted as a low-risk observational cohort study. However, certain items in the questionnaire, such as those related to sexual behavior or HIV status, may be considered sensitive. To minimize potential risks, several protective measures will be implemented. All data will be collected anonymously and stored securely using an encrypted system with restricted access, ensuring that no personally identifiable information is recorded.

Participants will be informed of their right to skip any question they find uncomfortable and their right to withdraw from the study at any time without any negative consequences. Additionally, counsellor will provide continuous support by explaining study procedures and addressing participants' questions throughout the study period. If necessary, participants will be referred to mental health or HIV-related services for appropriate care.

In cases where participants are found to be HIV positive, they will receive preliminary counseling and be referred to appropriate healthcare facilities for further testing and treatment in accordance with the Ministry of Public Health guidelines.

A Data and Safety Monitoring Board (DSMB) will also be established to oversee the project's risk management strategies, monitor participant safety and well-being, and ensure continuous ethical compliance. The DSMB will operate independently to review study procedures and provide recommendations to the research team regarding any necessary protocol adjustments to maintain ethical and safety standards throughout the study.

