## 2.6. Data management

Data collection will be carried out through the Qualtrics platform, where key items will be configured with mandatory responses and skip logic will be applied to ensure that participants are directed only to questions relevant to their previous answers. Once data collection is completed, the dataset will be exported, cleaned, and analyzed using STATA software.

Participant records across follow-up periods will be matched using the nicknames and phone numbers provided to the research team. All identifying information will be safeguarded through a dual-encryption system and stored on secure, password-protected servers maintained by Mahidol University. Access to these data will be limited to authorized study personnel, including the Principal Investigator (PI) and designated data managers responsible for overseeing data handling procedures.

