#### 3.4 Secondary Outcomes

- **HIV incidence:**

Number of new HIV infections per 100 person-years, based on STOS testing results and self-reported data during follow-up.

- **Sexual risk behavior:**

Proportion of participants reporting condomless anal intercourse with male partners during the past 6 months, measured through self-reported survey data.

- **Health-related risk behaviors (mental health and substance use):**

Proportion of participants reporting mental health problems (e.g., depressive symptoms, suicidal risk) and frequency of substance use during the past 6 months, based on self-reported survey data.

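### Suicidal risk and depression are asked about in a self-completed online survey, but no described step follows from a positive answer in either arm

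*Combined protocol and SAP*

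**What the plan says.** SAP 3.2 lists a reduction in depression and suicidal risk among the secondary objectives. SAP 3.4 defines the outcome as "Proportion of participants reporting mental health problems (e.g., depressive symptoms, suicidal risk"), taken from self-report. Protocol 2.4.2 agrees in general terms: "The secondary outcomes include changes in sexual behaviors, mental health, and other psychosocial indicators over time". SAP 2.1 and Protocol 2.1.2 describe the instrument as a Qualtrics questionnaire that participants complete themselves, with rounds at baseline, 6 and 12 months.

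On what happens next, Protocol 2.5 says: "If necessary, participants will be referred to mental health or HIV-related services for appropriate care". For HIV it is more definite: "In cases where participants are found to be HIV positive, they will receive preliminary counseling", followed by referral to a health facility. Its examples of delicate questionnaire items are "such as those related to sexual behavior or HIV status, may be considered sensitive".

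Protocol 2.2 admits participants from age 16. Protocol 2.3.1 plans an ethics committee waiver of parental consent for those under 18, to avoid unintended disclosure of orientation or HIV status.

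Protocol 2.5 also describes the data as anonymous, with nothing recorded that identifies a person. Protocol 2.6 links records across rounds by nickname and telephone number and describes how identifying information is stored.

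**The concern.** A trial that asks young people about suicidal risk should say what it does when someone reports it. Here the referral promise depends on need, but nothing says which answer or score establishes need, who would notice it, or how soon. The contrast with HIV in the same section shows that the authors do pair a finding with a response where they have thought one through.

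The stake is participant safety. For those aged 16 and 17 the waiver, which has a good reason, means that a parent need not know of their participation, so the study's own procedures carry more of the burden.

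The anonymity wording matters less. Read alone, 2.5 suggests that an answer cannot be traced to a person. Section 2.6 shows that it can.

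**Working it through.** No arithmetic applies. The check is whether any described step starts from an answer on suicidal risk or depression.

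1. **What is asked, and of whom.** SAP 3.2 and 3.4 name suicidal risk, and SAP 2.1 makes the survey self-completed. The survey is not limited to one arm, so all 100 planned participants (50 per arm) are covered. That the items recur at every round is suggested by Protocol 2.4.2, which speaks of change over time, and by the 6-month recall in SAP 3.4. It is not stated outright.

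2. **What each described step starts from.**
   - *Counsellor support (Protocol 2.5):* consists of explaining procedures and answering participants' questions.
   - *Retention contact (Protocol 2.1.3):* "Participants will be contacted regularly to receive project updates, appointment reminders, and encouragement to take part in each data-collection round". Its purpose is engagement.
   - *Staff contact at follow-up (Protocol 2.3.1):* staff check understanding and "verbally reconfirm consent before administering questionnaires or conducting STOS sessions". This precedes the questionnaire, so it cannot respond to that round's answers.
   - *STOS session (Protocol 2.1.1):* intervention arm only, and about the HIV test.
   - *Control-arm provision (Protocol 2.1.1 and 2.3.1):* a testing voucher and information on free hospital testing, both about HIV.
   - *Incident procedure (Protocol 2.7):* starts from an adverse or risk-related event. Whether a survey answer counts as one is not said.
   - *Raising a concern by Zalo or telephone (Protocol 2.7):* starts with the participant.
   - *DSMB (Protocol 2.5 and 4):* oversees risk strategy and reviews progress, safety reports and risk events at scheduled intervals.
   - *Survey logic and cleaning (Protocol 2.6, SAP 5.2):* skip logic routes questions. Cleaning looks at outliers, consistency, skip patterns and ranges.

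   None of these is described as following from a suicidal-risk or depression answer.

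3. **Comparison within Protocol 2.5.** An HIV-positive finding leads to counselling and referral. The mental health counterpart is a conditional promise whose condition is undefined.

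4. **Size.** The documents give no instrument, no cut-off and no expected frequency for suicidal risk. The number of positive answers, the number left without a response and the delay to any response cannot be derived.

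5. **Anonymity wording.** Section 2.5 says that nothing identifying is recorded, while 2.6 holds nicknames and telephone numbers and uses them for matching. Both cannot be right. SAP 2.1 is loosely worded but does disclose linkage by nickname and approved contact method.

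**The case against.** The strongest reply is that the plan is unspecific rather than silent. It commits to mental health referral, says that incident procedures exist, and has independent oversight. Need could well be judged from a survey answer, and the threshold, assessor and timing may sit in an operating procedure. The information sheet and consent script (annexes 7.1 and 7.2) were not available and are a natural place for crisis contacts. All of this stands, and it limits the claim to what the protocol and SAP describe. It does not supply the missing link between an answer and a response.

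Three stronger readings are tempting, and the documents do not support them.

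- *That nobody looks at answers until the study ends.* A reader might infer this from "Once data collection is completed, the dataset will be exported, cleaned, and analyzed using STATA software" in Protocol 2.6. That sentence concerns the analysis dataset. Protocol 2.1.1 uses screening answers to decide who proceeds and leaves out of the pilot anyone found HIV-positive after the survey. No study test has been described by then, so this most naturally means a reported status. Protocol 2.3.1 has staff contacting selected respondents afterwards. Individual answers are therefore used earlier for some purposes, earlier viewing is not barred, and no delay can be calculated.
- *That mental health items were judged not sensitive.* The two topics named in 2.5 are given as examples, not as a full list.
- *That staff must be alerted to each positive answer.* Counsellors are described for HIV testing and study questions. Their training and cover for suicide risk are not stated, so the documents do not show that this is feasible.

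It is also fair to say that a contact screen shown to everyone is not triggered by an answer. That is deliberate: it ensures that help is offered whenever the question is asked, without requiring staff who may not exist.

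**Conclusion.** The gap is real and concerns safety in both arms: suicidal risk and depression are elicited, and no described step responds to the answer. The plan, followed as written, could leave a positive answer unanswered. This is not evidence that anyone was or will be missed, and its frequency cannot be estimated.

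The conclusion rests on the protocol and SAP text as supplied, without annexes 7.1 and 7.2. If those list crisis contacts, the gap narrows, but the condition for referral stays undefined. A change is worth making because it costs little, and confidence is medium. The anonymity contradiction is certain on the text, but it is a separate wording matter and adds no weight to the safety point.

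**What to change.** **Main change.** At every remaining round, in both arms, add a Qualtrics screen after the suicidal-risk and depression items giving mental health and crisis service contacts. Show it to every respondent whatever the answer, so that the screen itself reveals nothing. The cost is one display page on a platform already in use. The downside is a possible small influence on later mental health answers. Because both arms see the same screen, it should not favour either.

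**Wording.** In Protocol 2.5, replace the anonymity statement with: confidential, and linkable by nickname and phone number. Align SAP 2.1 and check that participant-facing text agrees. This costs only an edit.

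**Option, not part of the recommendation.** If the clinical team confirms that suitably trained existing staff are available, it may choose to have positive answers flagged to a named role for discreet contact. The threshold and time limit are for that team. Staff time, possibly reduced disclosure and the risk of exposing 16- and 17-year-olds have to be weighed first.

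**If no rounds remain.** Protocol 2.3.2 and 4 describe withdrawals and DSMB meetings in the past tense, so this is possible. The wording correction still applies, and the trial report should state what response procedure was used for these items.

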## 2.6. Data management

Data collection will be carried out through the Qualtrics platform, where key items will be configured with mandatory responses and skip logic will be applied to ensure that participants are directed only to questions relevant to their previous answers. Once data collection is completed, the dataset will be exported, cleaned, and analyzed using STATA software.

Participant records across follow-up periods will be matched using the nicknames and phone numbers provided to the research team. All identifying information will be safeguarded through a dual-encryption system and stored on secure, password-protected servers maintained by Mahidol University. Access to these data will be limited to authorized study personnel, including the Principal Investigator (PI) and designated data managers responsible for overseeing data handling procedures.

## 2.7 Recording and reporting of risk events and incidents

If an adverse or risk-related event occurs during the study, the research team will systematically document and review the incident. Key information, including the type of event, the time it occurred, the individuals involved, and any immediate actions taken, will be recorded.

The research team will evaluate the seriousness of the incident and determine the appropriate follow-up steps. Any event deemed serious or potentially compromising participant safety will be promptly reported to the Data and Safety Monitoring Board (DSMB) for independent assessment and recommendations. These incidents will also be submitted to the Institutional Review Board (IRB) within the required reporting window in accordance with ethical guidelines.

Clear procedures are in place to ensure that all incidents are handled in a timely, transparent, and appropriate manner. All incident documentation will be securely stored and treated as confidential. Participants may also communicate any concerns or discomfort to the research team through the confidential communication channels routinely used in the study, including Zalo and telephone contact.

### 3. Funding

This study is funded by the National Institute of Mental Health (NIMH), under Grant R34MH123337.

#### 4. Monitoring and auditing

The Principal Investigator (PI) will oversee the full implementation of the study and ensure that all procedures align with the approved protocol and applicable ethical standards. Local field activities and data collection will be carried out with support from the Center for Applied Research on Men and Community Health (CARRMAH), a trusted community-based partner located in Ho Chi Minh City.

A Community Advisory Board (CAB) will contribute guidance on participant recruitment approaches and study operations to ensure meaningful community engagement and cultural appropriateness. Four CAB consultations were conducted and included representatives from NGOs such as HAIVN, community-based organizations including TestSGN, CARMAN, G3VN, and Galant clinics, as well as HIV testing and counseling staff and young men who have sex with men (YMSM).

Regular internal monitoring will be performed by the core coordination team to check data accuracy, review informed consent processes, and verify adherence to study procedures, including pre- and post-test counseling, data handling practices, and confidentiality safeguards. The Data and Safety Monitoring Board (DSMB) will independently review study progress, safety reports, and any risk events at scheduled intervals. The DSMB may also conduct audits to evaluate compliance with the protocol, ethical standards, and data quality. Three DSMB meetings were conducted with participation from the following experts: [name], PhD in Anthropology, Institute for Population and Social Research at Mahidol University; [name], PhD in Public Health and former Deputy Director of the Ho Chi Minh City Department of Health, now serving as President of the Vietnam Public Health Association and Consultant at Pham Ngoc Thach University of Medicine; and [name], PhD in Health Sciences and Vice Head of the Biostatistics and Informatics Department, Faculty of Public Health, University of Pharmacy and Medicine in Ho Chi Minh City.

All monitoring and auditing outcomes will be documented, and any deviations from the protocol will be addressed through appropriate corrective measures. Required reports will be submitted to the IRB and the DSMB, and all follow-up actions will be tracked to maintain ongoing quality assurance throughout the study.

#### 5. Publication and dissemination

Study findings will be disseminated through peer-reviewed publications and presentations at national and international conferences, following all ethical and reporting standards to ensure participant confidentiality. Summary results will also be shared with key stakeholders, including local health authorities, NGOs, service providers, and community-based organizations. Plain-language summaries and aggregated participant updates will be prepared to improve accessibility for non-academic audiences.

Given the intervention-focused nature of the study, the research team will engage multisectoral partners—such as government agencies, public health institutions, and community networks—to support the translation of findings into practice and explore opportunities for scale-up. Policy briefs may be developed to inform decision-making at local and national levels. Digital platforms may also be used to distribute summaries or infographics where appropriate.

The Community Advisory Board (CAB) will provide input to ensure culturally appropriate dissemination strategies. Authorship will follow international guidelines (e.g., ICMJE), and all dissemination materials will be reviewed and approved by the Principal Investigator before release.

## 1. Introduction

### 1.1 Objectives of the Statistical Analysis Plan

The primary objective of this Statistical Analysis Plan (SAP) is to prospectively define the analytical framework, statistical methods, and procedures that will be used to analyze data from the clinical study titled “HIV self-testing with online supervision (STOS) for Vietnamese MSM”. This SAP is designed to ensure that the analysis is transparent, reproducible, and aligned with the registered study protocol under ClinicalTrials.gov Identifier NCT05797961.

This SAP is intended to:

- Describe the planned analyses for the primary and secondary study objectives
- Specify the statistical techniques and data handling procedures to be used
- Define the analysis populations
- Outline approaches to address missing data, conduct sensitivity analyses, and implement subgroup analyses

### 1.2 Background and Significance of the Study

This study aims to evaluate the effectiveness of the STOS intervention in:

- Increasing the frequency of HIV testing (at least once every six months)
- Reducing sexual risk behaviors

The study is conducted as a pilot randomized controlled trial (pilot RCT) using a longitudinal cohort design among young men who have sex with men (YMSM Cohort, N = 100) residing in Ho Chi Minh City, Vietnam, with participants randomized into two groups: the STOS intervention group and the control group.

Given that YMSM in Ho Chi Minh City, Vietnam continue to have low rates of HIV testing, a high burden of HIV, and face structural and behavioral barriers to accessing healthcare services, this study is of significant public health importance and holds meaningful implications for national HIV policy development and prevention programming.

